### Blood endpoints;

- For the following endpoints, a statistical comparison will be performed between treatment groups at 6 months, using a linear model, with the endpoint as the dependent variable and treatment group, gender and baseline value as the explanatory variables. Data will be summarised descriptively and plotted graphically over time:
  - Percentage change in LDL
  - Change in atherogenic index
  - Change in high-sensitivity C-reactive protein
- Quality of Life endpoint: A statistical comparison will be performed between treatment groups for the change from baseline in the total IWQOL score at 6 months, using a linear model, with the change from baseline in total IWQOL score as the dependent variable and treatment group, gender and baseline score as the explanatory variables. Data will be summarised descriptively over time:
- Modifiable activity questionnaire;
  - Questionnaire responses from the modifiable activity questionnaire will be summarized per treatment group at 0 and 6 months for the following endpoints:
    - Total Physical Activity averaged over the past year in hours per week
    - Total Physical Activity averaged over the past year in MET-hours per week
- Concomitant medication adjustments
  - The changes in cardiovascular and/or initiation of diabetic medications will be summarized in terms of an increase, decrease or no change in concomitant medication, by treatment group. This assessment will be made by suitably qualified members of the study team. (It is not anticipated that any subjects will start the study on anti-diabetic medications as having diabetes mellitus is an exclusion criterion to

Neurovalens Limited Identifier: EXP18020

Clinical Study Identifier: 243973

enrolment, but it is possible that some may develop the condition during the course of the study).

Concomitant medications will also be summarized by treatment group according to
potential impact on weight status. These will be classified as medications that could
potentially cause either weight gain or weight loss as deemed by the Chief
Investigator.

In all secondary efficacy analyses which involve the use of linear, logistic or mixed effects repeated measures models, differences between groups will be evaluated using the LS mean difference between groups for continuous data, and an odds ratio between groups for categorical data. In both instances the 95% confidence intervals for the point estimates will be provided, along with the corresponding p-value for the hypotheses of a LS mean difference of 0 and an odds ratio of 1 respectively. Significance will detected using a 5% significance level, i.e. p-value <0.05.

For all efficacy outcomes, descriptive statistics will be produced based on the observed data for the absolute values at baseline and each post-baseline time point, as well as the change from baseline and (if relevant) percentage change from baseline to each time point.

### 12.2 Safety

The safety of the VeSTAL and Sham devices will be evaluated using descriptive summaries of safety data, with all analyses performed on the Safety Analysis Set.

A summary of treatment emergent Adverse Events (AE) and Adverse Device Events (ADE) will be provided for both the VeSTAL device and sham control treatment groups. Separate summaries will be provided, per treatment group, for any Serious Adverse Events (SAEs or SADEs) or causally related adverse events which occur on study.

Summaries of responses from the Adverse Event Monitoring Questionnaire at 1, 3, 6 months (where available), will be summarized per treatment group and time point. Additionally, the outcomes of hearing and ear canal assessments, performed at baseline, and 6 months will be summarized in order to detect any signs of deterioration which may occur whilst using the devices.

Laboratory data and vital signs as listed in section 2.2.3 will be summarized per treatment group at baseline and per time point on study. Additionally a summary of change from baseline for each of the laboratory tests will be presented over time.

Questionnaire responses for the quality of life – IWQOL-Lite questionnaire will be summarized per treatment group and time point.

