# Safety Endpoints

### Adverse Event Monitoring Questionnaire (At 1, 3, and 6-months)

Vestibular Stimulation to Trigger Adipe Clinical Trial Project Name	70 of 112		
Clinical Protocol for VeS			
243973(NI)_181094(UCSD USA) Study Reference Number		01 Document Number	11 Revision Number

Based on the survey of adverse events devised by Utz et al. (2011) occurrence of the following adverse events will be specifically enquired about by having the subjects complete the Adverse Event questionnaire: headache; pain/irritation behind the ears; vertigo/ dizziness; blurred vision; nausea; fatigue/ tiredness; seizures; tinnitus; and other symptoms. This will be done in person during the 3 and 6 months in person and at the 1-month timepoint, this questionnaire will be conducted via telephone or by email. It will also be completed on an ad hoc basis should the need arise. The questionnaire will ascertain if any of these symptoms occur during or after use of the device, and if so how frequently.

We will monitor each instance of an adverse event causing a dropout from the study. The dropouts, together with causes, will be recorded and reviewed at the end of the study. This guidance from the FDA will be followed: https://www.fda.gov/downloads/RegulatoryInformation/Guidances/UCM126572.pdf. If it becomes evident that the proportion of subjects who drop out due to safety concerns/ adverse events convincingly exceeds 30%, the study will be halted.

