# 20.6 Withdrawal criteria

These processes are to be implemented at both study sites.

Subjects who do not meet the screening criteria will be considered screen failures and will be replaced.

Vestibular Stimulation to Trigger Adip Clinical Trial Project Name	75 of 112		
Clinical Protocol for VeS			
Document Title			
243973(NI)_181094(UCSD USA)	Protocol	01	11
Study Reference Number	Document Type	Document Number	Revision Number

Subjects may withdraw from the investigation for any reason, at any time. Subjects are free to participate or not participate as they wish.

During the course of the study, subjects may be withdrawn from further involvement. Reasons for withdrawal may include:

- Subject removal of consent
- Any adverse event (related or not) that in the opinion of the investigator will endanger the well-being of the subject if they continued in the study.
- Poor compliance with the study requirements (protocol violation)
- Subjects lost to follow-up

All subjects withdrawn from the study due to unexpected device effect, directly related to the clinical investigation, will be followed-up and treated until the effect resolves.

Subjects who are withdrawn will not be replaced. All discontinuations will be documented along with the reason for withdrawal. Reasonable efforts will be made to contact any subject lost to follow-up during the course of the investigation in order to complete assessments and retrieve data. Should a subject be lost to follow-up the data available will be used in the final report, all uses of partial data will be documented. Ethics Committees and regulatory authorities will be notified of withdrawal as required by the regulations.

If possible, when a subject withdraws, or is withdrawn, a final visit should be conducted to allow a withdrawal discussion with the subject. At this visit the study device, iPod and any unused consumables should be collected. Also, at this visit it will be requested in a non-coercive manner if the subject will permit their weight to be taken, and if they are willing to complete the Adverse Event monitoring questionnaire. Moreover, if the subject had reached the point where they were due a follow-up appointment (i.e. at 3 and 6 months), then they be asked, again in a non-coercive manner, whether they are willing to have the scheduled tests and measurements for that appointment. It will though be made clear to the subject that these activities are optional on their part.

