If the subject does not wish to return for a final visit, then a withdrawal discussion on the telephone will be attempted. In this discussion factual information may be provided to the subject and arrangements made for end-of-study activities like return of study investigational device, payment of any outstanding compensation

Vestibular Stimulation to Trigger Adip Clinical Trial Project Name	76 of 112		
Clinical Protocol for VeS			
243973(NI)_181094(UCSD USA) Study Reference Number		01	11 Revision Number

and whether the subject will complete the adverse event questionnaire over the phone. There will be no attempt to coerce or unduly influence the subject.

A list will be assembled of all subjects who withdrew, or were withdrawn, from the study after enrollment. This will be broken down by center and treatment group and contain the following information: subject ID; specific reason for discontinuation; duration of treatment and last day of study adherence before discontinuation; whether or not the blind for the subject was broken at the time of discontinuation; if the subject returned the study device; and, after conclusion of the study and unblinding, what that subject's treatment allocation was – i.e. active device or sham.

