### 25. Adverse Events

### 25.1 General

In accordance with the European Standard BS ES ISO 14155:2011 the following definitions apply in relation to adverse events.

Adverse Event (AE). Any untoward medical occurrence, unintended disease or injury, or untoward clinical signs (including abnormal laboratory findings) in subjects, users or other persons, whether related to the investigational medical device. For subjects this definition relates to all study procedures and comparators, for users and other persons it relates only to the investigational medical device.

Adverse Device Effect (ADE). Adverse event related to the use of an investigational medical device. This includes adverse events resulting from insufficient or inadequate instructions for use, deployment, implantation, installation, or operation, or any malfunction and events resulting from intentional misuse of the investigational medical device.

Vestibular Stimulation to Trigger Adip Clinical Trial Project Name	84 of 112		
Clinical Protocol for VeS			
243973(NI)_181094(UCSD USA) Study Reference Number	Protocol Document Type	01 Document Number	11 Revision Number

Serious Adverse Event (SAE). An adverse event that

- a) Led to death,
- b) Led to serious deterioration in the health of the subject, that either resulted in
  - 1) A life-threatening illness or injury, or
  - 2) A permanent impairment of a body structure or a body function, or
  - 3) In-patient or prolonged hospitalization, or
  - 4) Medical or surgical intervention to prevent life-threatening illness, injury or permanent impairment to a body structure or function.

Planned hospitalization for a pre-existing condition, or a procedure required by the CIP, without serious deterioration in health, is not considered a serious adverse event.

Serious Adverse Device Effect (SADE). Adverse device effect that resulted in any of the consequences characteristic of a serious adverse event.

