### 26. Recording and Assessment of Adverse Events

All observed or volunteered adverse events (serious or non-serious) and abnormal laboratory findings, regardless of treatment group will be recorded in the subjects Case Report Form. For all adverse events, sufficient information will be obtained to permit 1) an adequate determination of the outcome of the event (i.e. whether the effect should be classified as a serious adverse event) and; 2) an assessment of the causal relationship between the adverse event and the investigational medical device or, if applicable, the other study treatment.

Adverse events or abnormal laboratory results felt to be associated with the investigational device or, if applicable, other study treatment or diagnostic products(s) will be followed until the event (or its sequelae) or the abnormal laboratory finding resolves or stabilizes at a level acceptable to the investigator-sponsor.

Vestibular Stimulation to Trigger Adipose Loss (VeSTAL) Clinical Trial				85 of 112
Clinical Protocol for VeSTAL				
	Document Title			
243973 USA)	(NI)_181094(UCSD	Protocol	01	11
	ence Number	Document Type	Document Number	Revision Number

Abnormal laboratory results will be assessed by the Chief Investigator and in the event these results require additional follow-up, the subject will be contacted by the Chief Investigator (via email) advising the subject to contact their General Practitioner (GP).

In accordance with the standard operating procedures and policies of the local Independent Ethics Committee/ Institutional Review Board the site investigator will report SAE's to the IRB/IEC.

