### 11. DESCRIPTIVE STATISTICS

## 11.1 Subject Disposition

A descriptive summary of subject disposition will be provided to summarize the number of subjects screened, randomized, treated and eligible for the ITT or Safety Analysis Set populations. Additionally, the number of subjects who have completed or discontinued treatment at the 6-month time point will be summarized, along with their reasons for discontinuation. In particular, those subjects who discontinue treatment or study follow up due to adverse events will be reported.

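### SAP 12.2 tabulates the adverse-event questionnaire only at 1, 3 and 6 months and gives ad hoc and withdrawal forms no place, so that table can understate solicited symptoms

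*SAP*

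**What the plan says.** **What is collected.** Protocol 18.3 (Safety Endpoints) schedules the questionnaire at 1 month by phone or email and at 3 and 6 months in person. It asks about headache, irritation behind the ears, dizziness, blurred vision, nausea, fatigue, seizures, tinnitus and other symptoms, whether they occur during or after device use, and how often. The same section adds: "It will also be completed on an ad hoc basis should the need arise". Protocol 20.6 adds two more occasions, both optional for the subject. At a final withdrawal visit subjects are asked "if they are willing to complete the Adverse Event monitoring questionnaire"; if they do not return, the phone discussion covers "whether the subject will complete the adverse event questionnaire over the phone".

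**What is tabulated.** SAP 12.2 says: "Summaries of responses from the Adverse Event Monitoring Questionnaire at 1, 3, 6 months (where available), will be summarized per treatment group", and it presents these by time point. It has no unscheduled or withdrawal category and no summary across time points. SAP 10.1 reports endpoint data by nominal time, with no rule for assigning an off-schedule form to a visit. For categorical data, SAP 9 shows subjects without a value in a Missing category and generally takes percentages over the analysis population.

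**What else covers symptoms.** SAP 12.2 also states: "A summary of treatment emergent Adverse Events (AE) and Adverse Device Events (ADE) will be provided", with separate summaries for serious and causally related events. SAP 11.1 says that "those subjects who discontinue treatment or study follow up due to adverse events will be reported". Protocol 26 sends adverse events to the case report form: "All observed or volunteered adverse events (serious or non-serious) and abnormal laboratory findings, regardless of treatment group will be recorded".

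**The concern.** The questionnaire is a safety endpoint in its own right: SAP 2.2.3 lists it separately from adverse-event frequency. Subjects who leave because of nausea, dizziness or headache, or who prompt an ad hoc form, are those most likely to report the symptom off schedule. Under SAP 12.2 as written, most of those forms reach no questionnaire table. If the device causes the symptoms, more of these forms would come from the active arm, and the active-minus-sham difference in the questionnaire table would shrink.

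The protocol's intent also points towards using these data. Protocol 33 says that data from treated subjects who withdraw enter the final analysis, and SAP 10.2 includes subjects who withdraw early. SAP 13, which lists changes from the protocol, does not mention setting any questionnaire aside. Without a rule, the programmer decides what to do with the forms, possibly after unblinding.

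**Working it through.** No figure in the plan is in dispute here, so there is none to reproduce. The check is a comparison of the sections, followed by a hypothetical scale.

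**1. Where each form goes**

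| Form (Protocol) | Place in SAP 12.2 questionnaire summary |
|---|---|
| 1, 3 and 6 months (18.3) | Yes, by group and time point |
| Withdrawal visit when a 3- or 6-month visit was due (20.6) | Probably, at that time point |
| Withdrawal visit at another time (20.6) | No rule |
| Withdrawal phone call (20.6) | No rule |
| Ad hoc (18.3) | No rule |

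**2. Effect on a tabulated rate**

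Let N be the number in the arm, s the number with a symptom, and k the number of those s who report it only off schedule. With N fixed (SAP 9):

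- rate using all forms = s/N
- highest rate the scheduled table can show = (s − k)/N
- shortfall = k/N

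With N = 100, the shortfall is k percentage points, whatever s is. The middle line is a maximum for any one time point, because a subject who reports on schedule need not do so at every visit.

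**3. Hypothetical scale**

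Inputs:
- N = 100 per arm: 200 planned subjects allocated 1:1, assuming that all of them enter the Safety Analysis Set.
- s = 17 active and 6.2% sham: an assumption, close to the 16.8% and 6.2% adverse-event rates of the one-hour stimulation study cited in Protocol 5.2. These are not six-month questionnaire rates.
- Sham is assumed to lose no reports.

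| k | Table shows (17 − k)/100 | Excess over sham, minus 6.2 |
|---|---|---|
| 0 | 17% | 10.8 points |
| 2 | 15% | 8.8 points |
| 5 | 12% | 5.8 points |
| 8 | 9% | 2.8 points |

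**4. How large k could be**

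The plan needs 180 subjects and allows 10% dropout: 180/(1 − 0.10) = 200, so 20 dropouts, or about 10 per arm. Taking k = 8 means that 8 of those 10 leave because of symptoms without reporting them on any scheduled form. That is an extreme case. Ad hoc forms from subjects who stay could add to k, but the documents give no basis for a number.

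**5. Other denominator**

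SAP 9 says that percentages are generally, not always, taken over the analysis population. If the table instead used only subjects still in the study, and the k subjects had left, the rates would be 15/98 = 15.3%, 12/95 = 12.6% and 9/92 = 9.8%. The picture barely changes.

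**The case against.** **The wider safety analysis already covers these events.** A reader might infer that the symptoms which made people leave are under-reported in the trial as a whole. The documents do not support that. The adverse-event and device-event summary is not tied to visits, discontinuations due to adverse events are reported, and Protocol 18.3 records dropouts with their causes. The adverse-event definition in Protocol 25.1 ("Any untoward medical occurrence, unintended disease or injury, or untoward clinical signs") is wide enough for a symptom behind a withdrawal. This objection stands, and it confines the point to the questionnaire table. It does not remove the point, because neither document says that a symptom ticked on the questionnaire is entered as an adverse event. Protocol 26 speaks of events observed or volunteered, and the discontinuation report carries no symptom profile.

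**Silence is not exclusion.** No text bars off-schedule forms, and the nominal-time convention could be used to assign some of them to a visit. That is fair: the accurate statement is that no rule includes them. But a convention that could be applied in several ways is not a rule.

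**The SAP follows the endpoint's own heading.** Protocol 18.3 labels the questionnaire as a 1-, 3- and 6-month measure, and the extra forms are optional. That explains the SAP text. It does not give the extra forms a use.

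**Dropouts do not vanish.** One might read the by-visit tables as describing only subjects still in the study. Under SAP 9, subjects without a form appear as Missing, so the loss is visible. They still count in the denominator and not as symptomatic, even where a form reporting the symptom exists.

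**The scale is assumed.** In the cited one-hour study, 12 of 17 events were mild and only 1 was severe, so many early symptom-driven exits are unlikely. This stands; the larger values of k are bounds and not forecasts.

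**Conclusion.** The point holds in a narrow form and is minor. The questionnaire summary in SAP 12.2 has no place for ad hoc forms or for most withdrawal forms, so it can understate solicited symptom rates, and more so in the arm with more symptom-driven dropout. The shortfall is 1 percentage point per affected subject in an arm of 100. In the hypothetical case of 17 symptomatic active subjects it runs from 2 to 8 points, with 8 extreme. This rests on a fixed denominator of 100, no loss of reports in sham, and symptoms that appear on no scheduled form.

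The result does not extend to the adverse-event, device-event or discontinuation tables. Safety is compared descriptively, so no test, success criterion, alpha or power is affected.

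**What to change.** In SAP 12.2, add for each questionnaire symptom a per-subject summary by arm of whether it was reported at any time after baseline. Use all scheduled, ad hoc, withdrawal-visit and withdrawal-phone questionnaires, over the whole Safety Analysis Set. Keep the by-visit tables.

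Subjects with more forms have more chances to report a symptom, so show the number of questionnaires per arm, split into scheduled and off-schedule, beside the new table. A further sentence saying whether questionnaire symptoms are also entered as adverse events would settle how the two outputs overlap.

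The cost is a short addition to the SAP and one extra descriptive table from forms that the protocol already collects. Data collection and subject management do not change.

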#### 12.3 Tolerability

Tolerability analyses will be performed on the Safety Analysis Set, which reflects the true treatment received by subjects. Of interest will be the device usage or exposure to treatment in terms of the time since randomization to study completion, withdrawal or the date of data cut off for subjects ongoing treatment at the time of the final analysis. The total number of device sessions performed over the course of the subject's study participation will also be summarized by treatment group.

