#### 1. INTRODUCTION

Neurovalens are conducting a randomized, double blind, sham controlled clinical trial to evaluate the efficacy and safety of non-invasive electrical vestibular nerve stimulation (VeNS), together with a lifestyle modification program, as a method of reducing excess body weight. The study will be randomized using a parallel assignment in a 1:1 active to control allocation, whereby the active group will use the vestibular nerve stimulation (VeNS) device, combined with a lifestyle modification program, and the control group will receive a sham device, combined with a lifestyle modification program. The study aims to recruit a total of 200 participants, across two or three sites, with a dropout allowance of 10% to generate a minimum of 90 active treatment and 90 control subjects. The study will be double blinded, meaning that both the subjects and outcome assessors will be blind to device assignment until the end of the visit at the 6 month timepoint.

For the purposes of the final analysis, the treatment assignment will be unblinded to all study personnel such that inferences can be made as to the efficacy and safety of the vestibular nerve stimulation (VeNS) device, in comparison to a sham control. The study will last approximately 6 months in total for each participant. The final analysis will be conducted at the 6 month timepoint. All subjects will cease involvement in the trial after the 6 month blinded period.

This document outlines the process followed by the study team to conduct the final analysis, along with the planned efficacy and safety analyses designed to fulfill the study objectives. As specified in the study protocol, it is noted that the criteria to meet the primary objective, to establish the clinical performance of the VeSTAL device stimulation effect in subjects who are overweight, differ between the EU and USA regulatory clearance pathways. As a result, this document clearly defines the proposed analyses and success criteria for both the EU and USA regulatory clearance pathways in the relevant sections. The secondary efficacy and safety objectives are shared by both regulatory pathways and therefore will follow the same analysis plan once the primary objective has been evaluated.

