#### 5. SAMPLE SIZE CONSIDERATIONS

The primary outcomes are percent total body weight loss from the start of treatment (as a percentage of baseline total body weight), and the proportion of subjects who lose at least 5% of their baseline total body weight. These outcomes will be assessed at the 6-month mark.

Power calculations are based on simulation (for full details see supporting documents EXP18006 Simulation Plan v4.1 and EXP18006 Simulation Report v1.0). Simulation assumptions were informed by pilot data and data from the Modius device as follows:

- 90Kg median baseline weight in both groups (log-normal distribution with CV=24%),
- 6.6% mean percent weight loss in the active group at 6 months (SD 3.9%),
- 3.1% mean percent weight loss in the control group at 6 months (SD 3.9%),
- correlation between baseline weight and weight loss at 6 months of 0.4.

Under these assumptions, with a sample size of 180 participants randomized 1:1 active: placebo, there is greater than 80% power to demonstrate both the weight loss mean and categorical acceptance criteria at the 6 month time point.

Under an assumption of no difference between active and control but the same assumptions around SDs and correlations there is <2% probability overall of a type-I error with this sample-size.

Anticipating a drop-out rate of 10%, we will plan to recruit n = 200 total subjects overall in the study across all sites.

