#### **Neurovalens Limited**

Identifier: EXP18020 Clinical Study Identifier: 243973

It is likely that some subjects will not utilize their device for the recommended 7, or even mandated 5, hours per week, and therefore a treatment response analysis will be performed which will identify the number of subjects per treatment group who fail to meet these requirements at least once on study. The treatment response analysis will further summarize the frequency of times that the mandated hours are not adhered to by calculating the percentage non-adherence as  $n_t/n_T \times 100$  whereby  $n_t$  is the number of weeks a subject fails to use their device for the mandated 5 hours per week and  $n_T$  is the total number of weeks the subject has been on the study. The treatment response analysis will be used to identify groups of subjects which have high (>75%) , medium (50-75%) and low (<50%) treatment adherence (defined as 100% - percentage non-adherence) and their percentage weight loss will be summarized by treatment and adherence group accordingly, at the 6 month time point.

The total number of hours a subject avails of the mentor support group (WST or CTM) over the course of the subject's study participation will be described using summaries of the categorical time spent per week (0, 0-2, 2-4, 4-6, >6 hours), per treatment group.

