## 13. CHANGES OF ANALYSIS FROM PROTOCOL

The analyses contained within this statistical analysis plan supersedes the analyses defined in the study protocol (May 26th 2019, Version 5). For clarity, a summary of deviations from the protocol are summarized, along with justification for the change.

Neurovalens Limited Identifier: EXP18020

Clinical Study Identifier: 243973

1. All terminology reference to treatment dose has been removed as subjects will not receive a specific dose of treatment, but rather use the device headset as demonstrated. The dose response analysis described in the protocol will be reference as a treatment response analysis within this statistical analysis plan and related documents thereafter. Additionally, the treatment response analysis (section 12.3) will be performed on the safety analysis set to reflect the treatment that subjects actually received as opposed to the Intention to treat population referenced in the protocol which reflects randomized treatment.

- 2. The protocol references using usage time as a covariate in the linear modelling of percentage fat loss from baseline. As a post baseline endpoint, it may be difficult to distinguish the relationship between percentage fat loss and usage time, due to a cause and effect relationship e.g. the subject may discontinue treatment as they think the treatment is not effective, which in turn means that their percentage fat loss is reduced. As a result, only baseline covariates will be used to adjust the percentage fat loss from baseline, in the same way that percentage weight loss from baseline is treated. As an alternative means of investigating the relationship between usage time and percentage weight or fat loss, a descriptive summary will be provided for weight and fat loss by categorical groups of usage adherence.

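### SAP 12.3 reports follow-up time as device exposure, and its on-study adherence denominator can place a diligent early leaver in the high-adherence group

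*SAP*

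**What the plan says.** Treatment exposure is part of the secondary objective in SAP 2.1, and duration of exposure is a listed tolerability endpoint in SAP 2.2.4. SAP 12.3 then describes usage as "exposure to treatment in terms of the time since randomization to study completion, withdrawal or the date of data cut off". It adds a second summary by arm: "The total number of device sessions performed over the course of the" subject's participation.

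For adherence, SAP 12.3 defines percentage non-adherence as n_t/n_T × 100. The denominator n_T "is the total number of weeks the subject has been on the study". The numerator n_t counts the weeks in which use falls short of 5 hours. Subjects are then grouped as "high (>75%) , medium (50-75%) and low (<50%) treatment adherence (defined as 100% - percentage non-adherence"), and 6-month percentage weight loss is summarized by arm within those groups.

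SAP 13, item 2, explains why usage time is no longer a model covariate: "the subject may discontinue treatment as they think the treatment is not effective". Descriptive summaries by adherence group are offered in its place.

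On the data available, Protocol 11.2 and 31.2 say that time-stamped session logs are kept. Protocol 11.2 adds that the logs hold the duration of each session and are kept for active and sham devices alike.

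**The concern.** Neither measure does quite what its label says. Duration of exposure ignores the last day of device use, so it cannot separate a subject who used the device throughout from one who gave up early and kept attending visits.

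The adherence percentage looks only at the weeks before withdrawal. Two subjects with identical device use can land at opposite ends of the scale, and the one who withdrew gets the better score. SAP 13 is worried about people who stop because they see no benefit. If such a person used the device fully until leaving, the adherence grouping offered as the alternative can place them in the high group.

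What is at stake is the accuracy of reported exposure, which is a stated secondary objective, and of the counts in each adherence category.

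**Working it through.** The plan states no exposure or adherence figure to reproduce, so the check applies its definitions to example subjects.

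**Inputs**
- Planned duration (SAP 1): "The study will last approximately 6 months in total for each participant". I take this as 26 weeks, which is an assumption.
- Weekly threshold: 5 hours (SAP 12.3). SAP 12.3 calls 5 hours mandated, whereas Protocol 18.3 calls 7 hours mandated. Those passages need reconciling, but the arithmetic below has the same form with either threshold.
- Dropout (SAP 5): "Anticipating a drop-out rate of 10%, we will plan to recruit n = 200 total subjects overall". Check: 180/(1 − 0.10) = 200, which agrees with the plan. Expected dropouts: 200 × 0.10 = 20.

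**Step 1: exposure.** For a subject who stays to month 6, exposure under SAP 12.3 is 26 weeks whenever device use stopped.
- Last use at week 3: 26 reported against 3 used, 26/3 = 8.7-fold.
- Last use at week 4: 26/4 = 6.5-fold.
- Last use at week 13: 26/13 = 2-fold.

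**Step 2: adherence for identical use.** Adherence = 100 − 100 × n_t/n_T. Both subjects use the device 6 hours a week for three weeks and then not at all.
- Withdraws at week 3: n_t = 0, n_T = 3, adherence 100% (high).
- Stays to week 26: n_t = 23, n_T = 26, adherence 100 − 88.5 = 11.5% (low).

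**Step 3: which leavers are affected.** For a subject leaving at week 4:

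| Weeks at or above 5 h | As written | Over planned 26 weeks |
|---|---|---|
| 4 of 4 | 100% (high) | 15.4% (low) |
| 3 of 4 | 75% (medium) | 11.5% (low) |
| 2 of 4 | 50% (medium) | 7.7% (low) |
| 1 of 4 | 25% (low) | 3.8% (low) |
| 0 of 4 | 0% (low) | 0% (low) |

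Only a leaver who met the threshold in every week scores 100%.

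**Step 4: how the effect fades with time.** For a leaver with no missed week, the planned denominator gives 8/26 = 30.8% (low), 13/26 = 50.0% (medium) and 20/26 = 76.9% (high). From week 20 on, both versions give the same category.

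**Step 5: number of subjects.** If no dropout used the device fully before leaving, 0 subjects score 100% in this way. If all did, 20 of 200 do. The documents do not say how leavers use the device before they leave.

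**Step 6: comparison with the per-protocol rule.** SAP 7 requires an average of at least 3.5 hours a week for at least four of the first 6 months. The leaver with four full weeks fails that rule and is nevertheless high-adherence in 12.3.

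**The case against.** The strongest reply is that the planned outputs, read together, hide little. A subject who stops but stays scores low on adherence and has few sessions. A leaver has a short exposure time and few sessions, and appears in the disposition table with a reason (SAP 11.1). Protocol 20.6 also requires a withdrawal list by treatment group that includes treatment duration and last day of adherence. This stands as mitigation, but it does not correct either measure or the adherence groups.

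The reply also has force against a simple replacement of the denominator. Adherence while participating and persistence in the study are different quantities, and a fixed 26-week denominator merges them. It would count a subject withdrawn for pregnancy, or by the investigator for an unrelated adverse event, as non-adherent. Similarly, the span from first to last session can overstate use, because one session in week 1 and one in week 26 would give full exposure. Both points stand, and the fix below allows for them.

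Three stronger readings are tempting, and the documents do not support them:
- **Early leavers as a class are scored fully adherent.** The week-4 table shows otherwise. Anyone who falls below 5 hours, or stops some weeks before formally withdrawing, accrues missed weeks.
- **The active arm will look more adherent than sham.** That needs withdrawal rates and pre-withdrawal usage by arm, and the documents give neither.
- **Imputed weights of leavers contaminate the high-adherence weight-loss summary.** SAP 12.1.1 and the close of 12.1.3 base descriptive summaries on observed data, and 12.3 specifies no imputation. On that reading most early leavers have no 6-month weight and would not enter those cells.

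**Conclusion.** The point holds within limits. Duration of exposure in SAP 12.3 is time on study, so a subject who stops in week 3 or 4 and stays is reported with about 26 weeks. The adherence formula can give 100% to a leaver whose pattern of use would score 11.5% in someone who stayed. Between 0 and 20 of 200 subjects could score 100% in this way at the planned dropout.

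The result assumes a 26-week study and dropout at the planned 10%. The consequence is limited to descriptive tolerability and adherence tables. Neither regulatory pathway's success criteria and none of the labelling-claim tests uses these measures, and the per-protocol set has its own usage rule. The change is still worth making, because exposure is a stated objective and the data for a better measure are already collected.

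**What to change.** In SAP 12.3:
1. Derive duration of exposure from the device logs as first to last logged session, and report total logged hours with it, so that a single late session cannot pass for sustained use.
2. Move time from randomization to completion or withdrawal to the disposition summary, labelled as time on study.
3. Keep on-study adherence, and add beside it a labelled row with the planned 26 weeks as denominator. The first shows adherence while participating. The second also reflects persistence, and should be read alongside the reasons for withdrawal.

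A sentence confirming that the weight-loss summary by adherence group uses observed 6-month weights would settle the remaining ambiguity.

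The cost is SAP wording and slightly more programming from logs already held. Reported exposure and adherence become somewhat less favourable. The primary analysis is unchanged.
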